2.2 Secondary Objective

1. Evaluate uptake of PrEP
2. Evaluate adherence to PrEP
3. Evaluate uptake of buprenorphine when clinically indicated (HIPS site only)
4. Evaluate retention in buprenorphine programs (HIPS site only)
5. Assess change in risk behaviors at baseline, during, and after HCV treatment

6. Evaluate the impact of active IDU vs non-injecting opioid misuse on efficacy of DAAs for the treatment of HCV
7. Evaluate the impact of OST on HCV treatment outcomes

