3.1 Description of the Study Design

This is an open label, observational pilot study to evaluate a model of care for treatment of HCV in people with ongoing injection drug use through embedded clinics at HIPS in Washington, DC (Phase 1 and 2) and the UMDTC in Baltimore (Phase 2), and the IHV while offering collocated HIV preventive interventions when clinically indicated.

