3.4 Primary Hypothesis

The primary hypothesis is that a comprehensive model of care for individuals with high-risk sexual and drug use practices that incorporates standard of care HCV treatment with collocated PrEP and buprenorphine (when indicated) will result in high rates of HCV cure, as well as decreased incidence of HIV and HCV reinfection.

4 Study Population

Participants are individuals with chronic HCV infection and in the first phase (first 100 enrolled participants) ongoing injection drug use, defined as self-report of injection of a non-prescription drug within three months of screening visit, or in the second phase (enrolled participants 101-200) patients with self-report of opioid misuse within one year.

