4.2 Subject Inclusion Criteria

To be eligible for participation on this protocol, a participant must satisfy all of the following conditions:

1. Age ≥ 18 years old
2. Able and willing to sign informed consent
3. Chronically infected with HCV, defined as any individual with documentation of positive HCV antibody and positive HCV RNA test (HCV RNA of 2,000 IU/mL or greater).
4. Willing to have samples stored for future use
5. Ongoing opioid misuse: defined as self-report of either:
 - a. Phase 1 (first 100 enrolled participants) Injection of non-prescription opioids within three months of screening visit;
or
 - b. Phase 2 (enrolled participants 101-200) Use of non-prescription opioids within twelve months of screening visit

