13.1 Description of the Analyses

The primary outcome is achievement of SVR12 in phase 1 (first 100 enrolled participants). The primary analysis of efficacy for phase 1 is intention-to-treat for the proportion of patients who achieve SVR along with exact two-sided 95% confidence intervals, overall and by sub-categories. All patients who receive at least one dose of direct acting antiviral are included in the intention-to-treat analysis and patients without follow-up data are considered to have treatment failure. Chi-squared or Fisher's exact test will be used to assess the association of SVR12 with baseline characteristics such as HIV-status, as well as on treatment factors such as medication adherence and OST status. Percentage and standard error will be calculated for each of the secondary outcome of PrEP and buprenorphine including uptake, adherence, and retention. In phase 2, participants without recent IDU (opioid misuse within 1 year but not within 3 months) will be compared to patients with recent IDU, and the impact of collocated OST vs non-collocated OST will be assessed.

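### The Phase 2 group without recent injection is defined by recency of any opioid misuse, so recent non-injecting misusers fall in neither comparison group

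*Combined protocol and SAP*

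**What the plan says.** Section 13.1 gives the only visible rule for forming the Phase 2 comparison groups: "participants without recent IDU (opioid misuse within 1 year but not within 3 months) will be compared to patients with recent IDU".

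The other relevant text is:

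- **Phase 2 eligibility (section 4.2, item 5b).** Under the heading "Ongoing opioid misuse: defined as self-report of either", Phase 2 admits "Use of non-prescription opioids within twelve months of screening visit". Section 4 (Study Population) describes the same people as "patients with self-report of opioid misuse within one year". Neither text requires injection, and neither excludes use in the last 3 months.
- **The objective served (section 2.2, item 6).** "Evaluate the impact of active IDU vs non-injecting opioid misuse on efficacy of DAAs for the treatment of HCV".
- **The 3-month injection window.** Section 4 states the Phase 1 criterion as "injection of a non-prescription drug within three months of screening visit". Section 4.2, item 5a, states it as "Injection of non-prescription opioids within three months of screening visit".
- **Survey forms.** Appendix C is titled for people who injected in the last 3 months and Appendix J for people who did not. Their contents are not shown.
- **Sites.** Section 3.1 places HIPS in both phases and UMDTC in Phase 2 only.

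**The concern.** The group's name and its definition use different variables. The name depends on injection; the parenthesis depends on when opioids were last misused, by any route. If the parenthesis is coded literally, Phase 2 participants with current non-injecting misuse drop out of the comparison. They are the plainest members of the non-injecting side of Objective 6.

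This changes the question as well as the precision. The remaining group would contain only people with no opioid misuse for at least 3 months, set against people injecting within 3 months. A difference in SVR could then reflect stopping use as much as route of use.

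Two smaller gaps sit in the same sentence. It does not say expressly whether the recent-injection group comes from Phase 2 only. If Phase 1 were added, differences in site and enrolment period would enter the contrast. And sections 4 and 4.2 disagree on whether injection means any non-prescription drug or opioids only.

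**Working it through.** The plan gives no sample size, power or expected difference for this comparison, so there is no planned figure to reproduce. The check is one of group membership, followed by an illustration of size.

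**1. Who is assigned as written.** Describe each Phase 2 participant by four yes/no items on opioid use: injected within 3 months, injected 3 to 12 months ago, used without injecting within 3 months, used without injecting 3 to 12 months ago. Eligibility needs at least one yes, giving 2^4 − 1 = 15 patterns.

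| Pattern | Number of patterns | Group under 13.1 as written |
|---|---|---|
| Injected within 3 months | 8 | Recent injection |
| No opioid use within 3 months, some use 3 to 12 months ago | 3 | Without recent injection |
| Used within 3 months, but not by injection | 4 | Neither |

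Total: 8 + 3 + 4 = 15. Two of the 4 unassigned patterns involve no injection at all in the past year, which is exactly the non-injecting group of Objective 6. The patterns are not equally common, so 4 of 15 is not a share of participants.

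**2. Overlap.** No pattern falls in both groups when injection means opioid injection. Under section 4's wider meaning (any non-prescription drug), someone who injected a non-opioid within 3 months and last misused opioids 3 to 12 months ago would meet both definitions.

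**3. After redefinition.** Injection within 3 months and no injection within 3 months are complements. Every Phase 2 participant already meets opioid use within 12 months. With one meaning of injection, 0 of 15 patterns are unassigned and none is in both groups.

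**4. Illustrative size.** Assumptions: 50 of the 100 Phase 2 participants are recent injectors; SVR is 80% in them and 90% in the others. The values 80% and 90% appear in section 13.2, but not as expectations for these groups.

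Half-width of the 95% interval for the difference = 1.96 × √(0.9 × 0.1 / n_without + 0.8 × 0.2 / n_recent).

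| n_without | n_recent | Sum under the root | Half-width (points) |
|---|---|---|---|
| 50 (all included) | 50 | 0.00180 + 0.00320 = 0.00500 | 13.9 |
| 40 (10 lost) | 50 | 0.00225 + 0.00320 = 0.00545 | 14.5 |
| 25 (25 lost) | 50 | 0.00360 + 0.00320 = 0.00680 | 16.2 |
| 10 (40 lost) | 50 | 0.00900 + 0.00320 = 0.01220 | 21.6 |
| 50 (all included), Phase 1 added | 150 | 0.00180 + 0.00107 = 0.00287 | 10.5 |

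**The case against.** The strongest reply is that the parenthesis is shorthand for misuse within a year but no injection within 3 months. The label, Objective 6 and the titles of Appendices C and J all point that way, and outside section 13.1 the plan attaches a 3-month window only to injection. This reading is plausible and probably what was meant. It does not remove the problem: the sentence does not say it, and the parenthesis is the only operational definition in the visible text. Two analysts, one coding the label and one coding the parenthesis, would analyse different populations.

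Other points on that side stand in part:

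- The illustration rests on an assumed split and assumed losses. With 10 lost, the half-width moves only from 13.9 to 14.5 points. With a group of 10 and SVR of 90% there is one expected failure, so the normal approximation is poor and 21.6 is only a rough figure. Even with all 50 included, the half-width exceeds the assumed 10-point difference. The illustration also does not measure the change in population, which is the main harm.
- The sentence opens by limiting itself to Phase 2, so a Phase 2 comparator is the natural reading. That request is a clarification only.
- Splitting on injection within 3 months puts people who injected 3 to 12 months ago in the group without recent injection. This fits the label in section 13.1 but not a strict reading of non-injecting misuse in Objective 6.
- The contents of Appendices C and J are not visible, so any classification made on the forms cannot be checked.

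**Conclusion.** The concern holds for the rule as written. Section 13.1 leaves Phase 2 participants with non-injecting misuse, and no injection, in the last 3 months outside both groups, although Objective 6 needs them in its non-injecting group. This follows from the eligibility and analysis wording and needs no numerical assumption. How many people are affected cannot be derived; the half-widths above show scale only under the stated assumptions.

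It should be fixed, but its reach is limited: one secondary comparison in an observational pilot, with an intended meaning that can be inferred. The primary Phase 1 SVR12 analysis is untouched. Confidence is high on the mismatch itself; whether the analysis would in practice exclude these people is not known.

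**What to change.** Rewrite the sentence in section 13.1 so that both groups are defined by injection:

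- **Recent injection:** Phase 2 participants reporting injection in the 3 months before screening.
- **No recent injection:** all other Phase 2 participants, that is, opioid misuse by any route in the 12 months before screening and no injection in the last 3.

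Then:

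1. State whether the recent-injection group is Phase 2 only or also includes Phase 1.
2. Use one meaning of injection for this comparison. The wordings in sections 4 and 4.2 must be reconciled.
3. Optionally, report people who injected 3 to 12 months ago on a separate descriptive line, since Objective 6 read strictly would not count them as non-injecting.

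The cost is one sentence, provided that injection in the last 3 months is recorded at screening for every Phase 2 participant. The titles of Appendices C and J suggest that it is, but section 6.3.2 names only Appendix C at screening, so the team should confirm this.

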13.2 Sample Size Justification

Based on the available DAA drugs, we expect to be able to treat up to 200 patients for HCV, with primary efficacy analysis after the first 100 enrolled participants (phase 1). The SVR of the general US population for HCV-infected and non-injection drug users is estimated at >90%. We target in our population of injection-drug users no greater than a $\pm 10\%$ SVR difference from the standard 90% SVR. For the primary objective, we will have 85% power to reject the null hypothesis if the actual proportion of patients with SVR is 80% or higher at a 2-sided, $\alpha=0.05$ significance level.

14 Ethics/Protection of Human Subjects

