Co-Infection	Identifier for those with both HIV and hepatitis B or C
DAA	Directly Acting Antiviral
DC PFAP	DC Partnership for AIDS Progress
EMA	Ecological Momentary Assessment
GMA	Geographical Momentary Assessment
HCV	Hepatitis C Infection
HIPS	HIPS, Inc (partner site)
HIPAA	Health Insurance Portability and Accountability Act
GWU	George Washington University
ANCHOR	Study short name
HRPP	Human Research Protection Program
MSM	Men who have sex with men
NIH	National Institutes of Health
PWID	People who inject drugs
IHV	Institute of Human Virology
IRB	Institutional Review Board
MTA	Materials Transfer Agreement
N	Number (typically refers to number of subjects/sample size)
OST	Opiod Substittion Therapy
OUD	Opiod Use Disorder
PI	Principal Investigator
PrEP	Pre Exposure Prophylaxis
PRO	Patient Reported Outcomes
SAE	Serious Adverse Event/Serious Adverse Experience
SEP	Syrigne Exchange Program
SOM	School of Medicine
SUD	Substance Use Disorder
SVR	Sustained Viral Reponse
TDF/FTC	tenofovir/emtricitabine
UP	Unanticipated Problem
UPnonAE	Unanticipated Problem that is not an Adverse Event
RNI	Reportable New Information
UMDT	University of Maryland Drug Treatment Center (partner site)

Protocol Summary

Full Title:	A Novel model of Hepatitis C Treatment to Prevent HIV, Initiate Opioid Substitution Therapy, and Reduce Risky Behavior
Short Title:	ANCHOR
Conducted by:	Institute of Human Virology, University of Maryland
Principal Investigator:	[name]
Sample Size:	N= 200 for on-treatment (phase 1, n = 100; phase 2, n = 100); will enroll up to 400 for screening
Study Population:	Adults infected with HCV
Accrual Period:	48 months (24 months for phase 1 ; 24 months for phase 2)
Study Design:	This is an open label, non-randomized, observational pilot study to evaluate a model of care for treatment of hepatitis C in people with ongoing injection drug use. Participants will be treated with direct-acting antivirals (DAA) as per standard of care and will concomittantly be offered pre-exposure prophylaxis for HIV prevention and buprenorphine for treatment of opioid use disorder when clinically indicated.
Study Duration:	Start Date: September 2016 End Date: January 2022
Primary Objective:	To evaluate the efficacy of DAAs for treatment of hepatitis C in people with ongoing injection drug use.

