Some blood samples may be stored for future analysis in this research study. These samples will be stored by the IHV researchers and may be used in future research to learn more about HCV and HIV, the immune system and/or other related medical conditions. The blood will be used over time to gain a better understanding of the pathogenesis of HCV and HIV. Genetic testing will be performed. Different analytical and laboratory methods will be employed including but not limited to: PCR, ELISA, ELISPOT and immunohistochemistry; RNA/DNA, cytokine and antibody quantitation; viral particle detection and identification of genetic markers. The consent will include language for specimen storage.

8.2 Storage:

Samples will be kept in secure facilities with limited access. Samples and data will be stored using a unique identifier. Only investigators and study staff will have access to the samples and data.

GMA Data - Electronic data will be stored on secure password-protected computers. UMB has an executed Collaboration Agreement dated 5/1/18 with the National Institute on Drug Abuse (NIDA), National Institutes of Health (NIH) and will share some data as specified in the agreement with our scientific research partners at NIH. There will be no participant identifiers in the shared data.

8.3 Tracking:

Extra blood samples will be stored using a unique identifier that only the study team can trace back to the participants. These stored samples as well as a linkage file will be maintained in a database that will be managed by the Investigators and/or Study Coordinators and will be maintained on the IHV server. This database will also be stored on the password-protected computer of the Lead-Investigator/Study Coordinator in an encrypted and/or password-coded file.

8.4 Disposition at the Completion of the Protocol:

At the completion of the protocol (termination), samples and data will either be destroyed, or after IRB approval, transferred to another existing protocol. Final disposition of any samples cannot be done without written permission from the PI.

8.5 Reporting the Loss or Destruction of Samples/Specimens/Data to the IRB:

- Any loss or unanticipated destruction of samples or data resulting in a violation that compromises the scientific integrity of the data collected for the study will be reported to the IRB.

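### Section 13.2 names no null hypothesis, and its claim of 85% power at an SVR of 80% or more is untrue against both nulls the section implies (90% and 80%)

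*Combined protocol and SAP*

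**What the plan says.** Section 13.2 puts SVR in people who do not inject drugs at above 90%. It sets a target of no more than a 10-point "SVR difference from the standard 90% SVR" in either direction. It then states that "we will have 85% power to reject the null hypothesis if the actual proportion of patients with SVR is 80% or higher", at a two-sided 5% level. The primary efficacy analysis is on the first 100 enrolled participants (phase 1). The overall number is set by drug supply: "Based on the available DAA drugs, we expect to be able to treat up to 200 patients for HCV".

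Section 13.1 plans an analysis that is "intention-to-treat for the proportion of patients who achieve SVR along with exact two-sided 95% confidence intervals". Participants without follow-up data count as failures. It names no test and no comparison value. The primary hypothesis in 3.4 is qualitative (high cure rates) and gives no number. The Protocol Summary calls the study an "open label, non-randomized, observational pilot study".

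**The concern.** A power figure has meaning only relative to a null value and a direction of departure from it. Section 13.2 gives neither, so the 85% cannot be checked as written. The only values in the text from which a null can be built are 90% and 90% minus 10 points, or 80%.

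Neither fits the sentence. If the null is 90%, power falls as the true SVR climbs from 80% towards 90%, so *or higher* points the wrong way. If the null is 80%, a true SVR of 80% is the null itself, and the chance of rejection there is the type I error.

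This is the only power statement for the primary objective. A reader is told that power is at least 85% throughout the range the study hopes to see. A reader may also take failure to reject 90% as meeting the 10-point target, which it would not be.

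**Working it through.** **Inputs.** n = 100 (13.2, phase 1); reference SVR 0.90 and target difference 0.10 (13.2); two-sided alpha 0.05 (13.2); exact 95% limits (13.1). Assumption: all 100 enrolled participants take at least one dose and so enter the analysis.

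**Formulas.** Normal approximation in the direction of the true value: power = Φ((|p1 − p0| − 1.96·√(p0(1 − p0)/n)) / √(p1(1 − p1)/n)). Exact: find the counts whose Clopper-Pearson 95% interval excludes p0, then sum their binomial probabilities at p1. The table gives both tails together.

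**Reproducing the 85%.** With p0 = 0.90 and p1 = 0.80, √(0.09/100) = 0.03 and √(0.16/100) = 0.04. Then (0.10 − 1.96 × 0.03)/0.04 = 0.0412/0.04 = 1.03, and Φ(1.03) = 0.848. This matches the stated 85%.

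**Exact rejection region against 90%.** The upper limit is 89.8% at 83/100 and 90.6% at 84/100. The lower limit is 88.7% at 95/100 and 90.1% at 96/100. So 90% is rejected at 83 or fewer, or 96 or more. At a true 80% the rejections come from the lower tail, with probability 80.8%. A rejection there shows that SVR is *below* 90%.

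**Exact rejection region against 80%.** 71 or fewer, or 89 or more. The lower limit is 79.98% at 88/100 and 81.2% at 89/100.

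**Probability of rejection, normal approximation (exact in brackets):**

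| True SVR | Null 90% | Null 80% |
|---|---|---|
| 78% | 93% (91%) | – |
| 80% | 84.8% (80.8%) | 5.0% (3.3%), type I error |
| 82% | 71% (64%) | – |
| 85% | 40% (33%) | 21% (16%) |
| 88% | 12% (9%) | – |
| 90% | 5.0% (4.4%), type I error | 76% (70%) |
| 92% | 8% (9%) | – |
| 95% | 34% (44%) | – |
| 97% | 74% (82%) | – |

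**Where 85% is reached.** Null 90%: at a true SVR of 80.0% or lower (exact 79.3%), and again only from 97.5% upward (exact 97.2%). Null 80%: only from 90.8% upward (exact 91.4%).

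**Is there a null that makes the sentence true?** Yes, at about 66%: exact power at a true 80% is 86.9% for a null of 66% and 81.1% for 66.5%. No such value appears in the documents.

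**Does non-rejection of 90% meet the target?** Take 85/100. z = (0.85 − 0.90)/0.03 = −1.67, p = 0.096, so 90% is not rejected. The exact 95% interval is 76.5% to 91.4%. It also contains 90%, but it includes values below 80%, that is, shortfalls of more than 10 points.

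**The case against.** The strongest reply is that little rests on the sentence. The study is an observational pilot, its size follows drug supply, and 13.1 plans an estimate with an interval and no test against 90%. No stopping rule or success criterion uses the 85%, and the planned interval would itself show a shortfall. This stands, and it limits the consequence. It does not make the stated power correct.

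A second reply is that the number is not miscalculated: it reproduces, and against 90% the sentence is about right at exactly 80%. That is so by the normal approximation (with the exact limits of 13.1 it is 80.8%). The error lies in the missing null and in the words *or higher*.

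A third is that the sponsor's null is inferred. Continuity-corrected and arcsine versions of the 90%-versus-80% calculation give 81.7% and 81.0%, and a null near 66% cannot be ruled out as what was meant. This is fair, and it bears on the remedy: the sponsor must say which null was intended. A null that the documents do not contain cannot support the claim as it stands.

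Finally, quoting 85% and 81% side by side could suggest one test computed two ways. The z-test rejects 90% at 84 or fewer, or 96 or more. Its actual binomial power at a true 80% is 87.1%, with a type I error of 6.4%. The point is good: the corrected text should carry one method and one figure.

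**Conclusion.** The concern holds. No null is stated, and the sentence is untrue against both values that can be derived from 13.2. The 85% is reproduced only as the power to show that SVR is below 90% when it is 80%. That is the opposite of showing that SVR lies within 10 points of 90%. At a true SVR of 90%, where a reader would expect at least 85%, the probability of rejection is 4% to 5% against a 90% null and 70% to 76% against an 80% null.

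The figures assume 100 treated participants. With fewer, the normal-approximation power for 80% against 90% is 83.3% at n = 95 and 81.6% at n = 90. The primary estimate and its interval are unaffected. It should be fixed, since the error is clear and the correction is small.

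**What to change.** Reword the one sentence in 13.2 so that it states the null, the direction and a single method, and remove *or higher*. If the null was 90%, wording consistent with 13.1 would be: with 100 treated participants and exact two-sided 95% limits, there is about 81% power to show that SVR is below 90% if it is truly 80%; failure to show this is not evidence that SVR is within 10 points of 90%. If the sponsor had another null in mind, state it and recompute the figure. This changes no analysis, adds no decision rule and needs no more patients.

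A criterion that does address the 10-point target is possible but optional: an exact 95% lower limit above 80%, which needs at least 89/100. Its power is 70% at a true SVR of 90%, 90% at 92% and 99.6% at 95%. That would be a new rule, needing an amendment made before phase 1 results are known. The documents do not show whether there is still time. The Protocol Summary gives a September 2016 start and 24 months of phase 1 accrual, and section 8.2 already cites a "Collaboration Agreement dated 5/1/18".
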